2. GENERAL ANALYSIS DEFINITIONS

2.1. Visit Windows and Phase Definition

Figure 1: Schematic Study Overview: Option A

Abbreviations: LD: loading dose; MD: maintenance dose; RSV: respiratory syncytial virus.

- a. Subjects randomized to placebo will be subsequently randomized in a 1:1 ratio to the placebo regimen matching Regimen A or Regimen B.

Phases will be constructed as follows:

Trial phase	Start date	End date
Pre-screening	Date time of first assessment, taken as part of standard of care within 84 hours* prior to randomization	1 minute before start of screening phase
Screening	00:00 of the date of signing the informed consent	1 minute before the first study medication intake
Treatment	Date time of first study medication intake	Date time of last investigational medication intake + 72 hours
Follow-up	End of Treatment phase + 1 minute	Trial termination date (date of last contact) with timestamp 23:59.

*In order to account for “approximately” 72 hours prior to randomization

The last phase, whichever it is for a subject, always ends on 23:59 of the day of trial termination (last contact) in study 64041575RSV2004. Note a subject can volunteer for long-term follow-up, in this case the subject will be enrolled in study 64041575RSV2002.

Assessments will be assigned to phases based on their date time, seconds will be ignored. If the day part of the start date of the assessment is present but the time part is missing, the assessment will be allocated as if it started at 00:00h on the day of the assessment (unless for Adverse Events see details in section 6.1.1). If the day part of the end date of the assessment is present but the time part is missing, no formal imputation will be done, but these rules will only be applied in order to be able to allocate assessments to phases. The assessment will be allocated as if it happened at 23:59h on the day of the assessment.

As subjects do not always adhere to the protocol visit schedule, the following rules are applied to assign actual visits to analysis visits. Listed below are the visit windows and the target days for each visit.

All visits (regardless the investigated parameter) will be allocated to analysis visits based on the day relative to the start of study medication:

Target Day	Analysis visit (numeric version)	Analysis visit	Day Interval
$-\infty$	-1	Screening	≤ 1 ¹
1	0	Baseline	≤ 1 ²
1	1	Day 1	[1] ³
2	2	Day 2	[2]
3	3	Day 3	[3]
4	4	Day 4	[4]
5	5	Day 5	[5]
6	6	Day 6	[6]
7	7	Day 7	[7,9]
10	10	Day 10	[10,12*]
14	14	Day 14	[12*,20]
$+\infty$	28	Day 28	[21, $+\infty$ [

¹ Records before the datetime of first intake only.

² As calculated according to the baseline definition.

³ Includes only the post-dose records.

* Depending on the VISIT label, the measurement of subjects returning on Day 12 should be assigned to Day 10 or Day 14. In case the VISIT label equals Day 12 the measurement will be allocated to Day 10.

For the analyses of measurements scheduled once daily the following rules will be applied in order to have only one evaluation per subject per analysis visit:

1. If two assessments fall within the same interval, the measurement closest to the target day will be used.
2. If the assessments are equidistant, the last measurement within the interval will be used.
3. If there are two measurements on the same date and time, then the measurement with the highest sequence number will be used.

An exception will be made:

1. In case multiple nasal swabs were taken on a single day, the maximum viral load on the log scale will be used as the analysis value for that subject on that day.

For the analysis of measurements scheduled more than once daily (vital signs: twice daily and SpO₂: every 4 hours / every 8 hours), the assessments will be allocated to analysis time points as described in the table below based on the actual time of the measurement. In case there is more than one assessment per analysis time point window, the mean of these assessments will be calculated in order to have only one evaluation per analysis timepoint.

Analysis time point (numeric version)	Analysis time point	Time Interval (hour:min)
Vital sign assessments *		
1	Morning]02:00, 14:00]
2	Evening]14:00, 02:00]
SpO ₂ **		
0	Morning]0:00, 08:00]
8	Midday]08:00, 16:00]
16	Evening]16:00, 0:00]

* In case the measurement should be allocated to 'Evening' of the previous day based on the time interval, the analysis visit should be adapted based on the relative day of the previous day. In case less than 75% of subjects is inpatient on an analysis visit, the records will not be allocated to any time point. In this case, the average of all records on that day (selected according to the rules for the analysis visit defined above) will be used for the analysis in case multiple records are available. In case 75% or more subjects are inpatient on this analysis visit, all records will be assigned to an analysis time point (also subjects for which the visit is outpatient) and both time points will be analyzed.

** For the SpO₂, the analysis time point will be set to Midday on outpatient visits of individual subjects, without taking the actual time into account. In case at least 75% of subjects is still in inpatient on this analysis visit, all 3 time points will be used and shown in the analysis. In case less than 75% of subjects is inpatient, only the Midday time point will be analyzed.

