9. STUDY EVALUATIONS

9.1. Study Procedures

9.1.1. Overview

The [Time and Events Schedules](#) summarize the frequency and timing of efficacy, PK, biomarker, medical resource utilization, health economic, and safety measurements applicable to this study. There are 2 [Time and Events Schedules](#): 1 schedule for subjects who are hospitalized (up to their hospital discharge); 1 schedule for subjects after they are discharged from the hospital. Repeat or unscheduled samples may be taken for safety reasons or for technical issues with the samples.

The eCOA device will be provided to the parent(s)/caregiver(s) at screening to record the parent(s)/caregiver(s) ratings of the severity of the subject's symptoms (PRESORS) (see [Attachment 5](#)). The parent(s)/caregiver(s) will complete the eCOA twice daily (in the morning and in the evening); after Day 14, eCOA will be completed once daily in the evening (at approximately the same time each day) until the end of the study for subjects who have been discharged from the hospital. Whenever possible, the same parent(s)/caregiver(s) should

complete the eCOA throughout the study. The first parent/caregiver assessment on Day 1 needs to be recorded predose, before the LD. If the screening assessment was performed less than 8 hours prior to the LD, the predose assessment does not need to be performed. The first postdose parent/caregiver assessment must be performed between 6 and 12 hours after the LD (on Day 1 or Day 2, depending on the time of LD).

The investigator/study-site personnel will provide sufficient information to enable the parent(s)/caregiver(s) to complete the parent(s)/caregiver(s) eCOA and will ensure that the eCOA is completed correctly and on schedule to avoid missing or incorrect data.

Prior to completing the screening assessment, the parent(s)/caregiver(s) must complete a training module (included as part of the eCOA device) on how to enter responses to questions in the eCOA device. Study-site personnel will review the completion of the parent(s)/caregiver(s) eCOA on a daily basis.

The clinician eCOA ([Attachment 5](#)) will be completed by the investigator twice daily for the entire duration of hospitalization and once daily at the Day 7, Day 10, Day 14, and Day 28 visits during outpatient follow-up.

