9.1.4. Posttreatment Phase (Follow-up)

Days 7 to 28

Subjects will be evaluated for a total of 28 days after randomization. If they are not hospitalized they will be required to return to the hospital for follow-up assessments as an outpatient on Day 7, Day 10, Day 14, and Day 28 as indicated in the [Time and Events Schedules](#). On Day 28 all subjects will complete the study either as an inpatient or outpatient.

Should the study drug duration be increased to up to 10 days (following review of the data by the IDMC, refer to Section [11.10](#), Independent Data Monitoring Committee), additional study drug may be provided if needed. If a subject is discontinued from study drug, a follow-up visit will be scheduled 2 days (+2 days), 5 days (+2 days), 9 days (+2 days), and 23 days (±2 days) after the last dose of study drug was administered. Assessments should be performed as indicated in the [Time and Events Schedules](#), respectively for the Day 7, Day 10, Day 14, and Day 28 visits.

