9.7. Safety Evaluations

Safety and tolerability will be evaluated throughout the study from signing of the ICF onwards until the last study-related activity (end of study/early withdrawal).

An IDMC will be established to monitor the safety of subjects and will review data in an unblinded manner on a regular basis to ensure the continuing safety of the subjects enrolled in this study. The IDMC will review the data and make recommendations to the Sponsor Committee, which will be responsible for identifying appropriate actions based on the recommendations of the IDMC. Details regarding the IDMC are provided in [Section 11.10](#), Independent Data Monitoring Committee.

Any clinically relevant changes occurring during the study must be recorded on the AE section of the eCRF.

Any clinically significant abnormalities persisting at the end of the study/early withdrawal will be followed by the investigator until resolution or until a clinically stable endpoint is reached.

Safety assessments will be based on medical review of AE reports and the results of vital signs/SpO₂ measurements, ECGs, physical examinations, clinical laboratory tests, and other safety evaluations at specified timepoints as described in the [Time and Events Schedules](#). The results of unscheduled clinical/safety evaluations performed as part of routine clinical care while the subject is hospitalized will be collected in the eCRF for safety and/or clinical evaluation.

In the event that at least 2 invasive procedures such as a blood draw, mid-turbinate nasal swab, vital signs assessments, and/or ECG are required at the same time, the order of completion should be ECG first, then vital signs/SpO₂, then mid-turbinate nasal swab, then blood draw, with the blood draw for PK being obtained as close to the scheduled time point as possible.

The study will include the following evaluations of safety and tolerability according to the timepoints provided in the [Time and Events Schedules](#).

Adverse Events

Adverse events will be reported by the parent(s)/caregiver(s) or the subject's legally acceptable representative for the duration of the study. Adverse events will be followed by the investigator as specified in Section 12, Adverse Event Reporting.

Clinical Laboratory Tests

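### The Day 28 analysis visit has an infinite target day, so any later record of the same parameter in the database takes the Day 28 place in by-visit summaries

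*SAP*

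**What the plan says.** SAP 2.1 (Visit Windows and Phase Definition) maps records to analysis visits by study day: "All visits (regardless the investigated parameter) will be allocated to analysis visits based on the day relative to the start of study medication". In its table every post-baseline visit except Day 28 has its nominal day as target. Day 28 has a target of plus infinity and an interval from Day 21 with no upper limit.

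For measurements scheduled once daily, two rules reduce several records to one. First: "If two assessments fall within the same interval, the measurement closest to the target day will be used". Then: "If the assessments are equidistant, the last measurement within the interval will be used". The visit label is used only to place a Day 12 record. No rule prefers the scheduled Day 28 record or removes unscheduled ones.

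The protocol's Time and Events Schedules put the Day 28 visit at plus or minus 2 days, as end of study. Protocol 9.1.4 adds: "On Day 28 all subjects will complete the study either as an inpatient or outpatient". Two provisions can generate later results. Under Protocol 9.7, clinically significant abnormalities still present at the end of the study "will be followed by the investigator until resolution or until a clinically stable endpoint is reached". Protocol 9.1.1 allows extra sampling: "Repeat or unscheduled samples may be taken for safety reasons or for technical issues with the samples". In SAP 2.1 the last phase runs to the date of last contact, not to the Day 28 visit.

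**The concern.** A row labelled Day 28 should describe children at about Day 28. Nothing routine is scheduled afterwards, so a later record would come mostly from safety follow-up, in children whose abnormality had not settled. That follow-up stops at resolution or stability, so the last record will often be better than the scheduled one.

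SAP 6.2.2, 6.3.2 and 6.5.2 summarise actual values and changes from baseline by treatment group at each scheduled time point, with mean graphs over time. What is at stake is whether the Day 28 point in those displays holds the Day 28 value or a later one, with substitution concentrated in the children of most safety interest.

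**Working it through.** The plan states no figure to reproduce, so the check applies the two selection rules to the Day 28 window.

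**Inputs.** Target plus infinity, interval Day 21 onward, closest-to-target rule and last-on-tie rule (SAP 2.1). Scheduled visit on Days 26 to 30 (Protocol, Time and Events Schedules).

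**What an infinite target does.** Read literally, every record is infinitely far from the target. All records tie and the second rule takes the last. Read as a very large finite day, the latest record is closest and the first rule takes it. Both readings give the same selection:

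| Days with a record | Selected, target plus infinity | Selected, target 28 |
|---|---|---|
| 28, 35 | 35 | 28 |
| 28, 35, 42 | 42 | 28 |
| 27, 60 | 60 | 27 |
| 30, 33 | 33 | 30 |
| 24, 28 | 28 | 28 |

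**When the scheduled value is lost.** Pair each scheduled day (26 to 30) with one extra record on any other day from 21 to 60: 5 x 40 - 5 = 195 pairs.
- Target plus infinity: the scheduled value is displaced whenever the extra record is later, in 34 + 33 + 32 + 31 + 30 = 160 pairs, and never when it is earlier.
- Target 28: it is displaced in 4 + 2 + 0 + 1 + 3 = 10 pairs (visit on Day 26, 27, 28, 29, 30 respectively). In all 10 the extra record lies on Days 27 to 30, inside the protocol's own visit window.

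These pairs map possibilities; they do not estimate how often this would happen.

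**Size for one child, on assumed values.** ALT is 6 x ULN on Day 28 and 1 x ULN on Day 42, and the Day 42 result is in the database. The child's Day 28 entry becomes 1 x ULN. With 60 children per arm contributing (the planned number, SAP 1.2.1), the arm mean falls by (6 - 1)/60 = 0.083 x ULN. With 40 per arm (the minimum of 120 split 1:1:1), it falls by 5/40 = 0.125 x ULN.

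**Which displays are reached.**
- Biochemistry and ECG: both scheduled at Day 28 and summarised by visit.
- Swab viral load: sampled at Day 28 and described by visit.
- Vital signs: when under 75% of subjects are inpatients, SAP 2.1 averages the records of one day, and that day is chosen by these same rules.
- Hematology and urinalysis: no scheduled Day 28 sample, so no Day 28 value exists to displace. A late record would instead create one.
- Unaffected: the primary model, which uses Days 2 to 7 (SAP 5.2.3); the AUCs to Day 10 and Day 14; the worst-grade and worst-abnormality tables (SAP 6.2.1, 6.3.1, 6.5.1); and the listings.

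**The case against.** The strongest reply is that displacement needs a later record of the same parameter in this study's database, and the documents do not promise one. Protocol 9.7 has the investigator follow persisting abnormalities. It commits to eCRF entry of unscheduled routine-care results only while the child is hospitalised. Long-term follow-up is a separate study. This stands as a condition: later records are possible, neither guaranteed nor excluded.

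Second, the by-visit summaries are specified for scheduled time points, and the SAP names unscheduled records where it wants them, as in the laboratory listing and the worst vital-sign and ECG abnormalities. That could mean unscheduled records stay out of the summaries. SAP 2.1, however, allocates all visits by day and states no such exclusion, so the text is ambiguous at best.

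Third, the infinite target mirrors the minus infinity given to Screening and may be a deliberate last-available-value convention. Even so, the output is labelled Day 28.

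A reader might infer that late toxicity would be hidden or made to look milder, always in the same direction. The documents do not support that. Follow-up may end at a stable but still abnormal value, and a child who worsens after Day 28 would contribute a worse one. An ALT of 6 x ULN is Grade 3 in the SAP's toxicity table (3.0 to 8.0 x ULN). It would still enter the worst-grade cross-tabulation, the listing of abnormal laboratory values and the separate listing of Grade 2 or higher values (SAP 6.2.2).

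**Conclusion.** The concern holds as a minor defect. The selection is certain: on either reading of an infinite target, the latest record from Day 21 onward is used. Its effect is conditional on a later record of the same parameter reaching the database and not being excluded as unscheduled. Such records are most likely in children followed for a persisting abnormality (Protocol 9.7 and 9.8). A shift toward resolved or stabilised values is therefore a reasonable expectation, but it is not guaranteed.

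The number of children affected cannot be derived from the documents. Only the Day 28 by-visit summaries and mean graphs are exposed. Safety is descriptive and untested (Protocol 11.8), and no primary result or worst-grade table changes.

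**What to change.** In the SAP 2.1 window table, set the Day 28 target day to 28 and close the interval at Days 21 to 35. State that records after Day 35 are assigned to no analysis visit and are used only in listings and worst-grade or worst-abnormality tables.

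This interval keeps the visits of children who stop study drug early, whose Day 28 assessments fall 23 (plus or minus 2) days after the last dose. A last dose on day d places that visit on Days d + 21 to d + 25: Days 22 to 26 for a Day 1 stop, Days 27 to 31 for Day 6, and up to Day 35 for Day 10 under extended treatment.

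Do not use the protocol's Day 26 to 30 visit window as the analysis window. After a Day 1 stop it would catch only one of the five permitted days (Day 26), and after a Day 2 stop only two (Days 26 and 27).

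The cost is two table cells and one sentence, with no new data.

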2.2. Pooling Algorithm for Analysis Centers

If positive treatment effects are found in a trial with appreciable numbers of subjects per center, there should generally be an exploration of the heterogeneity of treatment effects across centers, as this may affect the generalizability of the conclusions. As it is expected that for this trial subjects will be recruited over a large number of centers with a small number of subjects per study center, there is no need to check for treatment by center interactions. In addition, the primary endpoint is an objective endpoint, which is evaluated by a central viral monitor, and thus, no heterogeneity across centers is anticipated. Therefore, no pooling algorithm for analysis centers will be specified.

2.3. Analysis Sets

2.3.1. All Randomized Analysis Set

Randomized Analysis Set (RAND): All randomized subjects with a randomization date at or before the date of first intake of medication, or with a randomization date and a missing date for first medication intake, analyzed as randomized.

2.3.2. Efficacy Analysis Set(s)

Intention-To-Treat (ITT) set: All randomized subjects who receive at least 1 dose of study drug. Analyses on the ITT Set will be analyzed as randomized.

Intention-To-Treat-infected (ITT-i) set: All randomly assigned subjects who receive at least 1 dose of study drug and who have an RSV infection confirmed by a PCR-based assay at baseline or within 1 hour after the first study medication intake at the central laboratory. Analyses on the ITT-i Set will be as randomized.

Per-Protocol (PP) Analysis set: All subjects in the ITT-i set who do not have protocol violations that may have an impact on the efficacy analysis.

Decisions regarding which subjects are included in the PP set will be made before database lock on following criteria:

- Compliance: Subjects must have at most 1 missed dose. On the day of randomization at least one dose needs to be taken (so missed dose cannot be the first dose).
- The actual treatment must be the same as the planned treatment.
- No unblinding may have taken place during the study.
- Subjects will be excluded from the PP set if they have taken concomitant medications that may have affected the efficacy of the trial medication. Subjects will be excluded on a case by case basis using a list provided by clinical.
- Subjects may not violate inclusion criteria 3 or 4, nor exclusion criteria 1, 3, 4, 5, 6, 9 or 10.

Analyses on the Per-Protocol set will be analyzed as randomized.

2.3.3. Safety Analysis Set

Safety Set or All Subjects Treated (AST): All subjects who received at least 1 dose of study drug, analyzed as treated.

Randomized or Treated (RT) set: All subjects who are in the Randomized Analysis Set (RAND) and/or the All Subjects Treated (AST) set. The Randomized or Treated Analysis Set (RT) will be used in all listings.

2.4. Definition of Subgroups

Following subgroups will be used for the Efficacy analysis (primary and selected secondary endpoints):

- Onset time of RSV symptoms (≤ 3 days, >3 days - ≤ 5 days)
- Baseline RSV subtype

- Region [Japan, non-Japan] Note: Japan region only includes subjects indicated as Japanese on the CRF.
- Baseline RSV Viral load [$\leq C \log_{10}$ copies/mL, $> C \log_{10}$ copies/mL] with C = rounded median
- Presence of underlying comorbidity (yes, no)

Medical review will be done immediately before data base lock on a list with unique coded medical history terms (MedDRA Preferred Terms) to indicate which subjects had comorbidities. The following list of comorbid disease will be identified and potentially analyzed for efficacy (in case at least 15 subjects are enrolled in each of the subgroups):

- Comorbid diseases for severe RSV disease
 - BPD (bronchopulmonary dysplasia) [Yes/No]
 - CHD (congenital heart disease) [Yes/No]
 - Other Congenital disease [Yes/No]
 - Down syndrome [Yes/No]
 - Neuromuscular impairment [Yes/No]
 - Cystic fibrosis [Yes/No]
- Other conditions/therapy of potential interest due to risk of infections in general:
 - Type I diabetes [Yes/No]
 - Use of systemic corticosteroids (PO, IV) prior to or during the treatment phase

[Yes/No], based on medical review on a list with unique coded concomitant medications.

The following subgroups will be investigated for safety (complete safety for region, selected summary tables for age category):

- Region [Japan, non-Japan] Note: Japan region only includes subjects indicated as Japanese on the CRF.
- Age category [28 days-24 months; > 24 months to ≤ 36 months]

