In the statistical models following predictive covariates and or baseline indicators may be included: baseline \log_{10} viral load, smoking in the environment (yes/no), presence/absence of comorbid diseases, presence/absence of comorbid diseases associated with risk for lower respiratory tract disease, presence/absence of other conditions/therapy of potential interest, days since symptom initiation, RSV subtype, use of corticosteroids, supplemental oxygen at baseline, absence/presence of other viral or bacterial infections and age as continuous variable.

Stepwise forward selection will be used to identify the prognostic factors in combination with backward elimination. A significance value of 0.05 is required for a variable to enter the model and a significance value of 0.10 is required to stay in the model.

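### The optional corticosteroid subgroup counts steroids started after first dose, and the steroid covariate for the secondary models has no baseline limit

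*SAP*

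**What the plan says.** SAP 2.4 opens with five factors: "Following subgroups will be used for the Efficacy analysis (primary and selected secondary endpoints"). A second list, of comorbid diseases and other conditions or therapies of interest, is only "potentially analyzed for efficacy (in case at least 15 subjects are enrolled in each of the subgroups"). The last entry in that second list is "Use of systemic corticosteroids (PO, IV) prior to or during the treatment phase", a yes/no factor coded by medical review of the concomitant medications.

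SAP 2.1 starts the treatment phase at "Date time of first study medication intake" and ends it at "Date time of last investigational medication intake + 72 hours".

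The model building procedure in SAP 5.3.2 lists variables that may enter the statistical models by stepwise selection (enter at 0.05, stay at 0.10). They include "presence/absence of other conditions/therapy of potential interest", which is the SAP 2.4 group label that contains the steroid flag, and "use of corticosteroids, supplemental oxygen at baseline, absence/presence of other viral or bacterial infections and age as continuous variable". SAP 5.3.2.1 states that this procedure will be used for time to undetectable virus. For that endpoint, Protocol 11.3 provides only for additional covariates measured at baseline.

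**The concern.** A factor known before first dose splits the arms into groups that remain comparable by randomisation. A factor fixed partly by what happens after first dose does not. Protocol 3.2 expects that the drug may lessen severity and the need for supportive care, and Protocol 8 permits prescription drugs for the symptoms or sequelae of RSV. Steroid starts on study could therefore differ by arm because of treatment.

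Three consequences follow.

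- Within the yes and no groups, active and placebo children may differ in prognosis.
- Adjusting for the flag in a secondary model can remove part of the treatment effect, or create a difference where there is none.
- For times measured from first dose, the flag uses later information: a child who stays ill longer has longer to be given a steroid. Such a variable tracks outcome, so stepwise selection would tend to favour it.

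**Working it through.** **1. How far the flag reaches.** Ten doses given twice daily finish on Day 5 or 6 (Protocol 6). Adding 72 hours gives 5 + 3 = Day 8 or 6 + 3 = Day 9. The primary endpoint runs from baseline to Day 7, so the flag covers that whole window and one to two days more. If dosing is extended, it reaches further.

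**2. Which analyses it touches.**

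| Analysis | Steroid variable? |
|---|---|
| Primary mixed model (SAP 5.2.3) | No |
| Steroid subgroup (SAP 2.4) | Yes, if at least 15 subjects per level |
| Time to undetectable virus, interval-censored AFT model (SAP 5.3.2.1) | Yes; stepwise procedure invoked |
| Hospital stay and readiness for discharge, AFT model (SAP 5.3.2.3) | Unclear; only through the general wording of 5.3.2 |
| Logistic models (SAP 5.3.2) | Unclear, same reason |
| Clinical stability, Cox model (SAP 5.3.2.3) | No; covariates are named |

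**3. The plan's own effect size.** SAP 1.4 assumes a high-dose reduction in log viral load AUC of 30% with onset within 3 days and 20% later, with 40% of subjects in the first group: 0.4 × 30% + 0.6 × 20% = 24%. The SD is 34% of the placebo AUC. A normal approximation for high dose against placebo, with 60 per arm and one-sided 0.025, gives Φ((0.24/0.34) × √30 − 1.96) = Φ(1.91) = 97.2%. A simulation of the two-contrast test with Pocock-type spending (looks at 90, 120 and 180, the 90 being assumed) gives 96.1%. Both agree with the stated figure of about 97%, so these inputs represent the plan fairly.

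**4. What the flag does to a 24% effect.** I simulated 600,000 subjects per scenario. The assumptions, none of them in the documents, are: 5% to 20% have steroids before first dose; 10% to 20% start on study at the placebo mean AUC; the odds of starting rise by a factor OR per SD of viral AUC. Results for 10% before first dose and 20% on study:

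| OR | Flag yes, placebo vs high dose | Effect, yes | Effect, no | Adjusted effect |
|---|---|---|---|---|
| 1 | 28.0% vs 28.1% | 23.9% | 24.1% | 24.0% |
| 1.5 | 28.7% vs 24.8% | 24.1% | 23.4% | 23.6% |
| 2 | 29.9% vs 23.7% | 24.4% | 22.5% | 23.0% |
| 3 | 32.0% vs 22.9% | 24.3% | 21.0% | 21.9% |

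Across the rate combinations at OR 3, the adjusted effect is 21.4% to 23.4%, a loss of (24 − 21.4)/24 = 11% down to (24 − 23.4)/24 = 2.5%. The no group shows 21% to 22% and the yes group 23% to 27%. With a flag limited to use before first dose, every estimate stays at 23.5% to 24.8%.

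**5. No true effect on AUC.** If treatment itself lowers steroid starts (OR 0.5 to 0.7) and starts also track AUC, the no group shows a spurious difference of about 1% to 3% of placebo AUC, against the drug.

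**6. A stronger link.** Let treatment lower a severity score by 0.25 SD, let log length of stay have slope 0.5 on severity, and give steroids when severity plus noise passes a threshold. With 25% placebo use, adjustment removes roughly 5% to 50% of the effect as the noise SD falls from 3 to 0. With noise SD from 2 to 0.5, it removes about 5% to 16% at 5% use and 2% to 8% at 2% use.

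**The case against.** The strongest case is that little depends on this variable. The subgroup is conditional on numbers and listed apart from the five that will be run. The primary model has no steroid term. The covariate line does not say on-study: RSV subtype, comorbidity and other infections also lack a baseline label there, and SAP 1 says the SAP is to be read with the protocol, which speaks of baseline covariates. On that reading the covariate needs only a clarifying word.

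Most of this stands as a limit on scope. It does not rescue SAP 2.4, where the on-study window is explicit. It also leaves the covariate line open, because the neighbouring oxygen item is limited to baseline and the list repeats the label under which the prior-or-during flag sits.

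Four stronger readings are tempting, and the documents do not support them.

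- *The primary result is compromised.* Its type I error and power do not depend on steroid use.
- *The estimates for hospital stay and clinical stability will be biased.* The clinical stability model names its covariates. For hospital stay, the section does not invoke the stepwise procedure, and a variable must still pass the entry threshold.
- *The loss is large.* One choice in step 6 (steroid use 24.8% on placebo, 19.2% on active) gives (0.124 − 0.078)/0.124 = 37%. That is a single point in a wide range, and the documents supply none of its inputs.
- *The bias always runs toward no effect.* The yes group in step 4 moved both ways.

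**Conclusion.** The point holds in a limited form. If the steroid subgroup is run as defined, it conditions on an event after first dose that treatment may affect, so it is not a randomised comparison for the primary or any secondary endpoint. The same variable is open to stepwise selection for time to undetectable virus, beyond what Protocol 11.3 allows, and may reach other AFT and logistic models.

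The direction of concern is clear and the size is not. It is nil if steroid starts are unrelated to the course of illness, modest under the AUC assumptions above, and larger if steroids follow severity closely and are common. That treatment alters steroid use is plausible from the protocol but is not quantified there. The matter is worth correcting before unblinding; it is no reason to doubt the primary test.

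**What to change.** In SAP 2.4 and 5.3.2, define the variable as recorded systemic corticosteroid use (oral or intravenous) started before first dose of study drug, yes or no. Apply the same limit to the candidate covariate for other conditions or therapies. Code it from the prior medication records: SAP 4.6 already classes a medication as prior by a start before first dose and says how missing start dates are treated. Report steroids started on study descriptively by arm.

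The cost is one definition, with no new data and no change to sample size or power. The drawback is incomplete capture: Protocol 8 records prestudy therapy only up to 7 days before first dose, while it accepts acute systemic steroids within 14 days before randomisation. A course that ended earlier than the 7-day window would be coded no, and the SAP should say so.
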